Pharmacology: Cromolyn sodium is available in multiple dosage forms including an oral form used for treating gastrointestinal disorders in hypereosinophilic disorders and in mastocytosis; ophthalmic drops for treating allergic conjunctivitis; a nasal spray for treating allergic rhinitis; an inhalant solution for treating asthma, and is prepared in a compounded topical cream for treatment of cutaneous mastocytosis. Oral cromolyn sodium is poorly absorbed and the bioavailability of inhaled (8%), ophthalmic (0.03%), and oral (not more than 1%) is low. In one study of the absorption of oral [14C] disodium cromoglycate only 0.4% of an oral dose (20 mg) appeared in the 24 hr urine sample and 83% was recovered from the feces. While intravenous administration resulted in approximately equal amounts (30-50%) being excreted via the urine and feces (Walker SR, Evans ME, Richards AJ, Paterson JW. The fate of [14C] disodium cromoglycate in man. J. Pharm. Pharmac. 1972; 24: 525-531)

VANICREAM (OTC)

Drug Class: Moisturizer; Vehicle for topical preparations

Mechanism of Action: Vanicream is used as a topical lubricant that does not clog pores and is not absorbed. It is used by itself as a moisturizer and for compounding of topically applied skin care products.

Pharmacology: Vanicream is formulated as an OTC preparation comprised of: purified water, white petrolatum, sorbitol solution, cetearyl alcohol, propylene glycol, ceteareth-20, simethicone, glyceryl monostearate, polyethylene glycol monostearate, sorbic acid, BHT. It is free of lanolin, fragrances, parabens and formaldehyde. Vanicream is compatible with numerous topical agents used for skin care.

2 Study Objectives

The primary objective of this study is to assess the effectiveness of twice daily application of trolamine salicylate 10%, sodium cromolyn 5%, and diphenhydramine 1% on symptoms resulting from cutaneous mastocytosis.

3 Study Design

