3.4 Primary Safety Endpoints

Minimal systemic absorption is expected with each of the active components. Safety endpoints to be measured at the initial and final visits and include Investigator and Participant observation of local skin tolerability including ratings of itching, swelling

stinging/ burning, and dryness on separate scales as none (0), mild (1), moderate (2), or severe (3).

4 Subject Selection Enrollment and Withdrawal

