7.2.1 Definition of response

Complete response:

Clinically significant SCORMA improvement in all 3 parameters of treated, involved skin: % skin involvement; activity or symptoms &/or

Improvement in all 3 SkinDex-16 domains (Emotions, symptoms, functioning) &/or Resolution of 75% of cutaneous lesions

Near Complete response:

Clinically significant SCORMA improvement in two of 3 parameters of treated, involved skin: % skin involvement; activity or symptoms and/or

Improvement in 2 SkinDex-16 domains (Emotions, symptoms, functioning) &/or Resolution of >50% of cutaneous lesions

Partial Response:

Clinically significant SCORMA improvement in one 3 parameters of treated, involved skin: % skin involvement; activity or symptoms and/or

Improvement in 1 SkinDex-16 domain (Emotions, symptoms, or functioning) &/or Resolution of >25% of cutaneous lesions

No response:

No significant SCORMA improvement in any of 3 parameters of treated, involved skin: % skin involvement; activity or symptoms and/or

Improvement in no SkinDex-16 domain (Emotions, symptoms, functioning) &/or Resolution of no cutaneous lesions.

*Additionally, for primary safety endpoints which will be scored as none, mild, moderate, or severe, the proportion of patients in each category at each follow-up time point will be estimated for each of the different safety endpoints. P-values of 0.05 or lower will be considered as statistically significant.

Handling of missing data

This is a prospective study and therefore we do not anticipate any missing data. In the event of any unexpected missing data, no attempt to impute this missing data will be made; missing data will simply be treated as missing in the statistical analysis.

Multiplicity

Since this is an exploratory pilot study, no adjustment for multiple testing is needed. P-value of 0.05 or lower will be considered as statistically significant.

Primary Hypothesis:

The study seeks to demonstrate the effectiveness and tolerability of a novel topical composition consisting of 3 components (diphenhydramine, aspirin and cromolyn sodium) in a neutral skin moisturizing cream (Vanicream) for the treatment of cutaneous lesions of mastocytosis. This will be determined by the proportion of participants who achieve complete or near-complete response utilizing the SCORMA Index, and SkinDex-16 QOL.

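### The only criterion stated for the tolerability half of the primary hypothesis is the efficacy response proportion; the safety data are collected but not tied to that conclusion

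*Combined protocol and SAP*

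**What the plan says.** The Primary Hypothesis in Section 7.2.1 reads "The study seeks to demonstrate the effectiveness and tolerability of a novel topical composition consisting of 3 components", and the sentence after the product description gives the criterion: "This will be determined by the proportion of participants who achieve complete or near-complete response utilizing the SCORMA Index, and SkinDex-16 QOL". No other criterion is stated for either half of the hypothesis.

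The response categories in the same section combine three routes with and/or wording: improvement in SCORMA parameters of the treated skin, improvement in SkinDex-16 domains, and the percentage of lesions resolved.

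Tolerability has its own measurements. Section 3.4 specifies "Investigator and Participant observation of local skin tolerability including ratings of itching, swelling", together with stinging/burning and dryness, each scored 0 to 3 at the first and last visits. The attached safety form has columns for Weeks 0 and 2. Section 8.2 requires all adverse events to be recorded. For analysis, Section 7.2.1 says that "the proportion of patients in each category at each follow-up time point will be estimated for each of the different safety endpoints", and the next sentence is "P-values of 0.05 or lower will be considered as statistically significant".

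Section 2 opens with "The primary objective of this study is to assess the effectiveness of twice daily application" and does not mention tolerability. The Study Summary objective and Section 3.1 name both effectiveness and tolerability.

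**The concern.** Read as written, the plan answers a two-part question with a one-part measure. The response proportion shows whether lesions, symptoms or quality of life improved. It does not show whether the cream irritated the skin. Because the response routes are joined by and/or, a patient whose lesions resolve by more than half can be a near-complete responder with stinging rated severe at Week 2.

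The significance sentence in the safety paragraph does not fill the gap. It gives a threshold but no null hypothesis, comparison, test or sidedness, and the plan sets no acceptable rate and asks for no interval. With 10 patients, an absence of significance says little.

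What is at stake is the tolerability statement in the report, and its use in designing the larger study that Section 7.1 has in view.

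**Working it through.** **1. Which data reach the tolerability conclusion?**

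- Response proportion (7.2.1): the stated criterion for the whole hypothesis.
- Local ratings (3.4): tabulated by severity category at follow-up; no link to a conclusion.
- Adverse events (8.2): recorded; no link.
- Withdrawal for an adverse event (4.4.1): a listed reason for discontinuing; no link, and the same section says that no data are collected for withdrawn subjects.
- Stopping rule (8.5): depends on an unquantified number of patients with severe dermatitis. It governs study conduct, not the conclusion.

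The tabulation is also limited. Week 2 is the only follow-up visit, so proportions at follow-up do not show change from Week 0. Itching is a symptom of the disease as well as a possible reaction, so a Week 2 rating alone cannot separate the two.

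**2. What could a 0.05 threshold show?**

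The plan has no safety calculation to reproduce: Section 7.1 gives 10 patients without a power or precision calculation, which is acceptable for a pilot. The signed rank test in Section 7.2.1 is named for SCORMA and SkinDex-16 only. *Assumption:* each item is compared between Weeks 0 and 2 with a two-sided exact sign test, n = 10, and no patient improves.

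With k patients worse and none better, p = 2 × 0.5^k:

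- k = 5: 2 × 0.03125 = 0.0625, not significant.
- k = 6: 2 × 0.015625 = 0.031, significant.

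The exact signed rank test, with zero changes dropped, gives the same p-values when all changes go one way.

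The chance of significance is therefore P(X ≥ 6) with X ~ Binomial(10, π), where π is the true worsening rate:

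| π | P(X ≥ 6) |
|---|---|
| 30% | 0.047 |
| 40% | 0.166 |
| 50% | 0.377 |
| 70% | 0.850 |

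For example, at 50%: (210 + 120 + 45 + 10 + 1)/1024 = 386/1024 = 0.377.

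A one-sided test would need only 5 worse (p = 0.5^5 = 0.031). The chances are then 15%, 37% and 62% at true rates of 30%, 40% and 50%.

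**3. Effect of withdrawals.** If 2 patients withdraw for a reaction and 5 of the remaining 8 worsen, 7 of 10 did not tolerate the cream, yet the test on the 8 gives p = 0.0625. If 5 withdraw, the smallest attainable p is 2 × 0.5^5 = 0.0625.

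**4. What would an interval say?** Exact (Clopper-Pearson) two-sided 95% limits for 10 patients:

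- 0 of 10: 0 to 1 − 0.025^(1/10) = 30.8%.
- 1 of 10: 0.3% to 44.5%.
- 2 of 10: 2.5% to 55.6%.
- 3 of 10: 6.7% to 65.2%.

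**The case against.** The strongest reply is that the hypothesis sentence is a drafting slip. Tolerability has named endpoints, a collection form and a planned tabulation, introduced as additional to response. Section 3.2 already treats the response proportion as the efficacy endpoint. A cream that stings or swells would show up in the tables. Much of this stands: the safety data will not be lost, and poor tolerability could be visible in the report. But the criterion as written does not refer to those tables, and no other sentence says what they are to decide.

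Second, local intolerance can lower the response. SkinDex-16 items 1 to 4 ask about itching, burning or stinging, hurting and irritation, and local SCORMA includes erythema, elevation and pruritus. This stands in part. The and/or wording still lets a patient qualify through another route.

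Third, a reader might infer that the plan will declare the cream tolerated whenever p exceeds 0.05. The documents do not support that. No passage says so, and nearly the same sentence recurs under Multiplicity, so it may be general text placed in the wrong paragraph. Nor would every before-after test miss harm: 6 of 10 worse with none better is significant, and a 70% true worsening rate would be detected 85% of the time under the assumed test.

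Finally, the 31% upper limit applies to any study with 0 events in 10 patients. It is the precision that the pilot accepts, not a result of this wording.

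**Conclusion.** The point stands as a mismatch between claim and criterion: the tolerability half of the primary hypothesis has no criterion of its own, and the one stated for it measures efficacy. This rests on the text alone and needs no statistical assumption. It should be fixed.

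The arithmetic supports a narrower statement: if non-significance were read as tolerated, that would be unsafe. Under the assumed two-sided sign test with nobody improving, the chance of significance is 5%, 17%, 38% and 85% at true worsening rates of 30%, 40%, 50% and 70%. These figures depend on a test that the plan does not name.

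A reader might conclude that a badly tolerated cream would be reported as tolerated. The documents do not go that far, since the ratings and adverse events are recorded and the severity proportions tabulated. They leave the conclusion without a rule.

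**What to change.** 1. **Section 7.2.1, hypothesis.** Split the sentence so that the response proportion judges effectiveness only.
2. **Section 7.2.1, tolerability.** Judge it descriptively in all treated patients by three counts: patients with a worse rating at Week 2 than at Week 0 on any Section 3.4 item; patients with a new moderate or severe rating; and patients withdrawn for a reaction. Give each with an exact 95% interval, and report investigator and participant ratings separately.
3. **Safety paragraph.** Delete the p-value sentence and state that non-significance is not evidence of tolerability.
4. **Section 2.** Add tolerability, to agree with the Study Summary and Section 3.1.
5. **Section 4.4.** Keep the reason for withdrawal and the safety data up to that point, and count a withdrawal for a reaction as not tolerated in the analysis. This also helps Section 7.3, which puts every treated participant in the primary analysis while Section 4.4.1 collects no data for those who withdraw.

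The Week 0 and Week 2 ratings are already planned in Section 3.4 and on the attached form. Sections 6.1, 6.5 and 6.6 do not list them by name, so adding them there would make sure that the baseline rating is taken.

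The cost is a change of wording and a small change in data retention, with no extra patients or visits. The tolerability statement becomes less favourable, with an upper limit of about 31% even if no patient has a reaction. If the team wants a pass/fail judgement, it must set the acceptable rate itself, because the documents give none.

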7.3 Subject Populations(s) for Analysis

Each participant who received the study drug will be included in the primary analysis regardless of study withdrawal for any reason. In the event of any study withdrawals, in secondary analysis we will examine the sensitivity of our results to the exclusion of patients who withdrew.

8 Safety and Adverse Events

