4.4 Early Withdrawal of Subjects

4.4.1 When and How to Withdraw Subjects

Patients are free to withdraw at any time and for whatever reason. No data will be collected for withdrawn subjects and withdrawn subjects will not be replaced. There will be no follow-up for withdrawn subjects. Pre-specified reasons for discontinuing include, but are not limited to, the following:

- Patient request: Patient decided that he/she did not want to continue (for any reason).
- •Adverse Event: Patient experienced a related or unrelated event that would interfere with the study objectives/evaluation
- •Lost to Follow-up: Patient did not come in for a visit and could not be reached by phone
- Treatment Failure: If in the Principal Investigator's judgment, the patient's condition required another form of treatment
- •Noncompliance: Patient is not complying with the protocol requirements (i.e. visit schedule, dosing, regimen, etc.); a patient is to be withdrawn if he/she misses two consecutive visits
- •Other: Any other reason

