7.1 Sample Size determination

Due to the pilot nature of the study, no formal statistical power/sample size calculations are necessary. The sample size of 10 patients will be sufficient for this pilot study to obtain a preliminary estimate of treatment efficacy and to generate data that will be useful in the design of a larger study.

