We will use the SCORMA index and SkinDex-16 as both continuous variables and categorical variables. Change in SCORMA and of SkinDex-16 from baseline to the 2week follow-up visit will be estimated using sample mean, median, standard deviation, interquartile range, and range. SCORMA and SkinDex-16 will be compared from baseline to the follow-up time point using a paired Wilcoxon signed rank test.

Interim Analysis

There will not be any interim analysis given the low risk profile of the study formulation.

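### For the paired SCORMA and SkinDex-16 tests, the only planned sensitivity analysis is redundant for anyone who leaves before Week 2, and the responder denominator is not stated

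*Combined protocol and SAP*

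**What the plan says.** Section 7.3 defines the analysis set: "Each participant who received the study drug will be included in the primary analysis regardless of study withdrawal for any reason". It then plans one check on withdrawals: "in secondary analysis we will examine the sensitivity of our results to the exclusion of patients who withdrew". No other sensitivity analysis appears in the plan.

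Four other statements determine what that check can do.

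- Sections 6.1, 6.5 and 6.6 schedule two visits, Week 0 and Week 2, so each patient has a single post-baseline measurement.
- Section 4.4.1: "No data will be collected for withdrawn subjects and withdrawn subjects will not be replaced". It adds: "There will be no follow-up for withdrawn subjects".
- Section 7.2.1, on missing data, rules out imputation and says that "missing data will simply be treated as missing in the statistical analysis".
- Section 7.2.1, after the primary hypothesis: "SCORMA and SkinDex-16 will be compared from baseline to the follow-up time point using a paired Wilcoxon signed rank test". Changes from baseline to Week 2 are also summarised descriptively.

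The primary hypothesis in 7.2.1 rests on the proportion with complete or near-complete response. The plan does not say whether a treated patient without Week 2 data stays in that denominator.

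**The concern.** A signed rank test on change needs both values of the pair. A patient who stops before Week 2 has only the baseline value and cannot contribute, whichever analysis set 7.3 names. The promise to include all treated participants cannot be kept for these tests, and the check then removes people who are not there.

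Section 4.4.1 lists adverse event and treatment failure among its six reasons for discontinuing, so some of the missing values may be poor outcomes. Section 7.2.1 also sets a threshold: "P-value of 0.05 or lower will be considered as statistically significant". With 10 patients, one or two missing pairs can decide on which side of it a result falls. A report could truthfully say that the SCORMA and SkinDex-16 tests were unaffected by excluding early withdrawals, although that agreement was certain before any data were seen.

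**Working it through.** The plan gives no power, effect size or dropout figure, so there is no stated number to reproduce. Section 7.1 sets N = 10 without a calculation. The threshold of 0.05 is from 7.2.1; its sidedness is not stated, and two-sided is assumed. The withdrawal count w, the responder count r and the change scores below are assumptions.

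**1. Paired test, withdrawals without Week 2 data.** Take illustrative changes of −12, −9, −7, −6, −5, −4, +3 and −2 in eight completers, with w = 2.

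- As planned: n = 8. The only positive change has rank 2, so the positive rank sum is 2. Three of the 2^8 = 256 sign patterns give a sum of 2 or less, so p = 2 × 3/256 = 0.0234. The mean change is −42/8 = −5.25.
- After excluding withdrawals: n = 8, p = 0.0234, mean −5.25.

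The two are identical, and would be for any set of completer values.

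**2. Responder proportion, withdrawals without Week 2 data.**

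- Treated as missing: r/(10 − w) in both analyses, so no change.
- Counted as non-responders: r/10 becomes r/(10 − w). With r = 4 this is 40% against 4/9 = 44% (w = 1), 4/8 = 50% (w = 2), 4/7 = 57% (w = 3) or 4/6 = 67% (w = 4). With r = 5 and w = 2, 50% becomes 5/8 = 63%.

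**3. Withdrawals with Week 2 data.** Add two patients withdrawn at the final visit after being scored, with changes of −8 and −10. All ten give p = 0.0059 and mean change −60/10 = −6.0. Excluding these two gives p = 0.0234 and mean −5.25. If both were responders, 6/10 = 60% becomes 4/8 = 50%. Here exclusion makes the result less favourable.

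**4. An analysis that does test an unfavourable assumption.** Suppose that all completers improve, and give each withdrawal a worsening that ranks above every observed change. Exact two-sided p, no ties among completers:

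| Withdrawals | Complete-case | Worst-rank |
|---|---|---|
| 1 | n = 9: 2/512 = 0.0039 | n = 10, worsening rank sum 10: 2 × 43/1024 = 0.084 |
| 2 | n = 8: 2/256 = 0.0078 | n = 10, worsening rank sum 9 + 10 = 19: 2 × 221/1024 = 0.43 |

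Here 43 and 221 are the numbers of the 2^10 = 1024 sign patterns with a rank sum of at most 10 and at most 19. If the two withdrawals share the tied rank 9.5, the sum is still 19 and p = 2 × 213/1024 = 0.42.

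**The case against.** A reader might infer that the exclusion analysis can only return the same or a better result, and so can never show that withdrawals matter. The documents do not support that, for two reasons.

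First, if withdrawals stay in the denominator as non-responders, the proportion moves visibly: 5/10 against 5/8 is a difference of 13 points. On that reading the all-treated figure is already the unfavourable case for the primary measure, and exclusion is an ordinary completers contrast.

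Second, some withdrawn patients may have Week 2 scores. Section 5.2 judges compliance by jar weight at the final visit and provides for withdrawing non-compliant patients. Section 6.5 lists SCORMA and SkinDex-16 at that same visit, ahead of the compliance review. The plan does not say that such scores are discarded. Exclusion could then move the results either way, as step 3 shows, so the analysis should be kept.

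Other points also carry weight. The trial is a small, exploratory, unpowered pilot; 7.1 claims no more than this: "The sample size of 10 patients will be sufficient for this pilot study to obtain a preliminary estimate of treatment efficacy". Section 7.2.1 anticipates no missing data. Adverse event and treatment failure are two of six listed reasons, so missing values need not be bad outcomes. A worst-rank assignment is a form of imputation and conflicts with 7.2.1 unless that sentence is amended.

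None of this rescues the check for a patient who leaves before Week 2: in the paired tests and change summaries it still compares a result with itself.

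**Conclusion.** The point holds in a limited form. For SCORMA and SkinDex-16 as continuous outcomes, the exclusion analysis is redundant for anyone who leaves before Week 2, and no planned sensitivity analysis puts an unfavourable assumption about withdrawals into those tests. For the responder proportion, exclusion of patients without Week 2 data leaves the figure unchanged or raises it, and the plan does not settle which. Exclusion is informative for the paired tests only where a withdrawn patient was scored at Week 2.

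The size depends on withdrawals that the documents do not predict. The moves from 0.0039 to 0.084 and from 0.0078 to 0.43 are worst-case bounds for one and two withdrawals with every completer improved, two-sided. They are not forecasts. With no withdrawals the issue does not arise.

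**What to change.** 1. In 7.3, keep the exclusion analysis. State that for the paired tests it is informative only for patients withdrawn after being scored at Week 2, and state how those scores are used. Label the paired tests and change summaries complete-case.
2. In 7.3, add a supportive worst-rank signed rank analysis of SCORMA and SkinDex-16. Each treated patient without a Week 2 value takes the largest worsening rank, with ties shared, and the result is reported beside the complete-case one. Amend the no-imputation sentence in 7.2.1 to allow this exception.
3. In 7.2.1 or 7.3, state that the primary proportion has all treated patients as its denominator and counts those without Week 2 data as non-responders.

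The cost is a few sentences and one extra run of a test already planned, with no new data or patients. The downside is a less favourable supportive p-value if patients withdraw.
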